During the treatment period, patients who are clinically stable at an initial RECIST 1.1-defined PD may continue to receive study treatment at the discretion of the Investigator and patient. A follow-up scan is to be collected after the initial RECIST 1.1-defined PD, preferably at the next (and no later than the next) scheduled imaging visit, and no less than 4 weeks after the prior assessment of PD and this scan is evaluated using the Confirmation of Radiological Progression criteria are outlined in Appendix E. If the subsequent scan does not confirm the immediate prior radiological PD, scanning should continue until the next RECIST 1.1-defined PD which in turn will require a subsequent scan evaluated using the Confirmation of Radiological Progression criteria outlined in Appendix E.

Follow up of patients post discontinuation of study drug

Patients who have discontinued treatment due to toxicity or symptomatic deterioration, clinical progression, or who have commenced subsequent anticancer therapy will be followed up with tumor assessments until RECIST 1.1-defined PD plus an additional follow-up scan or until death (whichever comes first) and followed for survival.

Survival

All patients in the study should be followed up for survival.

Statistical methods

All statistical analyses will be performed by AstraZeneca or its representatives (e.g. CRO).

A comprehensive statistical analysis plan (SAP) will be prepared and finalized within 3 months of the first enrolled patient, and any subsequent amendments will be documented, with final amendments completed prior to reporting of the data.

All analyses will be descriptive in nature. Categorical (e.g., gender) study measures will be reported using frequency and proportions and continuous measures (e.g., age) will be reported using mean, median, standard deviation and range. Additionally, Kaplan-Meier curves will be presented for time-to-event outcomes such as overall and progression free survival.

All analyses will be based on the intention to treat (ITT) population consisted of all enrolled patients who had received at least 1 dose of study drug (chemotherapy or Durvalumab). For the overall study population and for any subpopulation, estimated 95% CIs for various event rates will be calculated.

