9.3 Populations for analyses

Definitions of the analysis sets for each outcome variable are provided in Table 12.

Table 12 Summary of outcome variables and analysis populations

Outcome variable	Populations
Efficacy Data	
PFS, 6mPFS, 12mPFS	Safety analysis set
OS, 6mOS, 12mOS, 18mOS,	Safety analysis set
ORR, PROs, and symptom endpoints	Safety analysis set
DoR	Responders analysis set
TTD	Safety analysis set
PRO	Safety analysis set
Hospital resources	Safety analysis set
Demography	Safety analysis set
Biomarkers	Biomarkers Analysis Evaluable Set
Safety Data	
Exposure	Safety analysis set
AEs	Safety analysis set
Laboratory measurements	Safety analysis set
Vital Signs	Safety analysis set

AE Adverse event; XmPFS Proportion of patients alive and progression free at X months from inclusion; XmOS Proportion of patients alive X months from inclusion; ITT Intent-to-treat population; ORR Objective response rate; OS Overall survival; PFS Progression-free survival; DoR Duration of Response; TTD Time to Treatment Duration; PRO Patient-reported outcome.

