9.3.1 Safety analysis set

The safety analysis set will include all included patients that received at least one dose of study treatment. Safety, efficacy, and PROs data will be summarized using the safety analysis set. (Patients who were enrolled but did not subsequently go on to receive study treatment will not be included in the analysis.)

Responders Analysis Set: The subset of patients, within the Safety Analysis Set who are evaluable for response analysis and who achieve an objective response.

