### 3.3 Responders analysis set

Responders analysis set will include the subset of patients, within the Safety Analysis Set who are evaluable for response analysis and who achieve an objective response.

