#### Endpoints analyzed:

- Progression-free survival (PFS): This analysis will be performed for the Intention-to-Treat population (ITT). PFS is defined as the time from the first date of treatment until the date of objective disease progression or death (by any cause in the absence of progression) regardless of whether the patient withdraws from IP or receives another anticancer therapy prior to progression.

**PFS (days)** = Date of event or Censor date – treatment start date +1

Patients who have not progressed or died at the time of analysis will be censored at the time of the latest date of assessment from their last evaluable assessment. However, if the patient progresses or dies after 2 or more missed visits, the patient will be censored at the time of the latest evaluable assessment prior to the 2 missed visits. If the patient has no evaluable visits or does not have baseline data, he/she will be censored at Day 1 unless he/she dies within 2 visits of baseline, in which case the date of death is the event date.

The PFS analysis will be based on the programmatically derived RECIST 1.1 using the Investigator tumor assessments. It will be analysed PFS, PFS at 6 months (6mPFS) and PFS at 12 months (12mPFS).

- Objective response rate (ORR): This outcome will be analysed for the responder's analysis set. The ORR will be based on the programmatically derived RECIST 1.1 using the investigator tumor data.
- Duration of response (DoR): This outcome will be analysed for the responder's analysis set. DoR is defined as the time from the date of first documented response per RECIST1.1 until the first date of documented progression per RECIST1.1 or death in the absence of disease progression.

DoR (days) = Date of PFS event or censoring – Date of first response +1

The end of response should coincide with the date of progression or death from any cause used for the PFS endpoint. If a patient does not progress following a response, then the patients' DoR will be censored at the PFS censoring time. DoR will not be defined for those patients who do not have a documented response. It will be analysed DoR and DoR at 1 year (DoR12)

- Overall survival (OS): This analysis will be performed for the Intention-to-Treat population (ITT). OS is defined as the time from the first date of treatment until death due to any cause.

OS (days) = Death date or Censor date - treatment start date +1

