## **5. ANALYSIS METHODS**

Descriptive statistics will be used for all variables, as appropriate. Continuous variables will be summarized by the number of observations, mean, standard deviation, median, quartiles (Q1 and Q3), minimum, and maximum. Categorical variables will be summarized by frequency counts and percentages for each category. The number of missing data will be provided for every analysed variable.

Missing values will not be considered for calculating percentages or any other descriptive, meaning that only valid values will be presented. No use of any method for the handling of missing data is foreseen.

For patients excluded from the statistical analyses, descriptive of the reasons for non-evaluability will be provided.

The software package SAS version 9.4 will be used for data analysis.

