#### Endpoints analyzed:

- Progression-free survival (PFS): The PFS analysis will be based on the programmatically derived RECIST 1.1 using the Investigator tumor assessments. The analysis will be performed using Kaplan Meier plots. Summaries of the number and percentage of patients experiencing a PFS event will be provided along with median PFS and its 95% confidence interval. In addition, the proportion of patients who are progression-free at 6 (PFS 6) and 12 (PFS 12) months will be presented.

A subgroup analysis may be conducted comparing PFS in the following subgroups, assuming sufficient sample size per subgroup: platinum therapy receiving (carboplatin or cisplatin), age ( $\geq 65$ ,  $< 65$ ), gender, performance status, smoking status, CNS metastasis at baseline (Yes/No) and number of chemotherapy cycles (5 or 6 cycles vs 4 or less cycles)

For each subgroup, the HR and 95% CI will be calculated by Cox regression and a log-rank test will be provided.

- Objective response rate (ORR): The ORR will be based on the programmatically derived RECIST 1.1 using the investigator tumor data. Summaries will be produced that present the number and percentage of patients with a tumor response (CR/PR). 95% CI will also be presented.

A subgroup analysis may be conducted comparing ORR in the following subgroups, assuming sufficient sample size per subgroup: platinum therapy receiving (carboplatin or cisplatin), age ( $\geq 65$ ,  $< 65$ ), gender, performance status, smoking status, CNS metastasis at baseline (Yes/No) and number of chemotherapy cycles (5 or 6 cycles vs 4 or less cycles). Results will be compared using Chi-Squared test.

- Duration of response (DoR): DoR will be analyzed using the investigator tumor data in responding patients. Descriptive data will be provided for the DoR in responding patients (continuous data), including the associated Kaplan-Meier curves. In addition, the DoR at 1 year (DoR 12) will be analyzed.

A subgroup analysis may be conducted comparing DoR in the following subgroups, assuming sufficient sample size per subgroup: platinum therapy receiving (carboplatin

or cisplatin), age ( $\geq 65$ ,  $< 65$ ), gender, performance status, smoking status, CNS metastasis at baseline (Yes/No) and number of chemotherapy cycles (5 or 6 cycles vs 4 or less cycles)

For each subgroup, the HR and 95% CI will be calculated by Cox regression and a log-rank test will be provided.

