## **6.2 Handling of missing data**

Missing values will not be considered for calculating percentages or any other descriptives, meaning that only valid values will be presented. The number of missing data will be provided for every analysed variable. No use of any method or imputation of data for the handling of missing data is foreseen.

For the questionnaires EORTC QLQ-C30, EORTC QLQ-LC13 and PRO-CTCAE, for each subscale, if < 50% of the subscale items are missing, then the subscale score will be divided by the number of non missing items and multiplied by the total number of items on the subscales. If at least 50% of the items are missing, then that subscale will be treated as missing. Missing single items are treated as missing. The reason for any missing questionnaire will be identified and recorded. If there is evidence that the missing data are systematic, missing values will be handled to ensure that any possible bias is minimized.

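### The SAP analyses ORR in the responders set, against the protocol's own table; taken literally, ORR is 100% whatever the treatment does

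*SAP*

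**What the plan says.** SAP 4.2.2.1 assigns an analysis set to each effectiveness endpoint. PFS, OS and time to treatment discontinuation go to the ITT population. For response rate it says: "Objective response rate (ORR): This outcome will be analysed for the responder's analysis set". The next bullet assigns duration of response (DoR) to the same set. SAP 3.3 defines that set as patients within the safety analysis set "who are evaluable for response analysis and who achieve an objective response"; Protocol 9.3.1 defines it the same way.

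SAP 5.2.1 plans the number and percentage of patients with CR or PR, with a 95% CI, and optional subgroup comparisons: "Results will be compared using Chi-Squared test". It names no denominator.

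The protocol says otherwise. In Table 12 of Section 9.3 (outcome variables and analysis populations), the row "ORR, PROs, and symptom endpoints" is assigned to the safety analysis set, and only DoR to the responders set. Section 9.3.1 adds the general rule "Safety, efficacy, and PROs data will be summarized using the safety analysis set". The synopsis has a similar general rule, "All analyses will be based on the intention to treat (ITT) population consisted of all enrolled patients", limited to those who received at least one dose.

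On missing data, SAP 5 says: "Missing values will not be considered for calculating percentages or any other descriptive, meaning that only valid values will be presented". SAP 6.2 repeats the rule and adds: "No use of any method or imputation of data for the handling of missing data is foreseen".

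**The concern.** A response rate needs non-responders in its denominator. A set defined by having responded has none, so the analysis the SAP specifies carries no information about how often patients respond. ORR is a named secondary effectiveness endpoint in Section 3 of the protocol. Whoever programs it must either report a meaningless 100% or depart from the SAP and choose a denominator that the SAP does not name: all treated patients, or only those evaluable for response.

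That choice affects the result. The SAP does not say how to count treated patients whose assessments are all not evaluable (NE), or who have no scan after baseline. NE is a recorded RECIST 1.1 category in Appendix E of the protocol, so it is not a missing value. A patient who dies or leaves before the first scan has no response value at all, and the missing-value rule in SAP 5 and 6.2 could be read as removing that patient from the percentage. This would raise the reported rate relative to a count over all treated patients.

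**Working it through.** **Inputs**
- Numerator: patients with investigator-assessed CR or PR per RECIST 1.1, called R (Protocol 9.4, SAP 5.2.1).
- Denominator as the SAP assigns it: the responders set, which contains R patients (SAP 4.2.2.1 and 3.3).
- Denominator as the protocol assigns it: the safety analysis set, taken as N = 85, the planned size (Protocol 9.2, SAP 2.2).
- Values of R: assumed. Neither document gives an expected ORR. Section 2 of the protocol cites initial response rates of up to 70% with chemotherapy, and 60/85 = 70.6% is close to that. The lower values only show a range.

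**Check of the interval method.** The plan gives no ORR figure to reproduce. The exact (Clopper-Pearson) method can be checked against the adverse-event precision table in Protocol 9.2. 17/85 gives 12.1 to 30.1%, 21/85 gives 16.0 to 35.3%, 51/85 gives 48.8 to 70.5% and 60/85 gives 59.7 to 80.0%. All four intervals match that table.

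**ORR as the SAP is written.** ORR = R/R = 100% for any R of at least 1. When every patient in the set is a responder, the exact 95% lower limit is 0.025^(1/R) and the upper limit is 100%. For example, 0.025^(1/34) = 0.897 and 0.025^(1/60) = 0.940. The interval depends only on how many responders there are.

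**ORR in treated patients.** ORR = R/85, with the exact interval.

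| R (assumed) | Treated patients, R/85 (95% CI) | SAP text, R/R (95% CI) |
|---|---|---|
| 34 | 40.0% (29.5 to 51.2) | 100% (89.7 to 100) |
| 43 | 50.6% (39.5 to 61.6) | 100% (91.8 to 100) |
| 51 | 60.0% (48.8 to 70.5) | 100% (93.0 to 100) |
| 60 | 70.6% (59.7 to 80.0) | 100% (94.0 to 100) |

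**Subgroup test.** Suppose two subgroups have 40 and 15 responders. Within the responders set both have 0 non-responders. The expected non-responder count is the subgroup total times the non-responder total, divided by the overall total: 40 × 0/55 = 0 and 15 × 0/55 = 0. The chi-squared statistic divides by these expected counts, so it is undefined. The same holds for any pair of subgroups.

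**Unscanned patients.** If u treated non-responders are dropped because they were never scanned, the rate becomes R/(85 − u), which exceeds R/85 whenever u is above 0. The documents give no basis for a value of u, so the size of this bias cannot be estimated.

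**The case against.** The intention is easy to guess. A percentage, a confidence interval and a chi-squared comparison make sense only if non-responders are in the set. The sentence assigning the set is the same for ORR and for DoR, which suggests a copying slip, although the documents do not say so. A reported 100% would be noticed at once, Table 12 of the protocol already supplies the right set, and the study is descriptive with no hypothesis. This lowers the chance that a wrong figure is published. It does not remove the contradiction, and it leaves the replacement denominator to be chosen at analysis.

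Only Table 12 is specific to ORR. Section 9.3.1 and the synopsis are general statements; read strictly, the synopsis would also clash with the protocol's own use of the responders set for DoR. That is fair: Table 12 is the controlling conflict, and the other two are supporting.

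The handling of NE and unscanned patients is a weaker point. Excluding them is a possible reading of the missing-value rule, not a stated plan, and counting them as non-responders is a convention that neither document states. That stands, and the point is made here only as a clarification to include in the same edit.

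**Conclusion.** The concern holds. As specified, ORR is 100% by construction, its interval reflects only the number of responders, and the subgroup tests cannot be run. No other SAP text supplies a denominator, and the SAP contradicts the protocol's population table without giving a reason. The 100% result needs no assumption beyond at least one responder. The comparison figures rest on 85 treated patients and an assumed 34 to 60 responders. The true rate can still be counted by hand as responders over treated patients, but that is not the analysis the SAP specifies. This must be corrected before ORR is analysed.

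**What to change.** In SAP 4.2.2.1, change the analysis set for ORR from the responders set to the safety analysis set (all treated patients), and keep the responders set for DoR only. This follows Table 12 of the protocol. It also puts ORR on the same treated-patient basis as PFS and OS, because the ITT population in SAP 3.1 and the safety analysis set in SAP 3.2 both require at least one dose.

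In the same edit, add a sentence along these lines: *Treated patients without a CR or PR, including those whose post-baseline assessments are all NE and those with no post-baseline assessment, remain in the denominator as non-responders; the missing-value rule in Sections 5 and 6.2 does not apply to ORR.* This wording avoids the term best response, which neither document defines for this endpoint.

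The cost is SAP wording only, with no new data. The reported ORR will be lower than the current text would produce.

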7. DISCONTINUATION OF TREATMENT AND SUBJECT WITHDRAWAL

7.1 Discontinuation of study treatment

An individual patient will not receive any further durvalumab or EP dose if any of the following occur in the patient in question:

- Withdrawal of consent from further treatment with IP. The patient is, at any time, free to discontinue treatment, without prejudice to further treatment. A patient who discontinues treatment is normally expected to continue to participate in the study (eg, for safety and survival follow up) unless they specifically withdraw their consent to all further participation in any study procedures and assessments (see Section 7.3).
- An AE that, in the opinion of the Investigator or AstraZeneca, contraindicates further dosing
- Any AE that meets criteria for discontinuation as defined in the Dosing Modification and Toxicity Management Guidelines (see Section 8.4.5) or as defined in the local prescribing information for the EP treatment.
- Pregnancy or intent to become pregnant
- Non-compliance with the study protocol that, in the opinion of the Investigator or AstraZeneca, warrants withdrawal from treatment with IP (eg, refusal to adhere to scheduled visits)
- Initiation of alternative anticancer therapy including another investigational agent
- Clinical progression or confirmed radiological progression (refer to 0E) and Investigator determination that the patient is no longer benefiting from treatment with IP

- Completion of the study by the sponsor for obtaining the indication for ES-SCLC in combination with etoposide + platinum

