7.1.1 Procedures for discontinuation of study treatment

Discontinuation of study treatment, for any reason, does not impact the patient's participation in the study. A patient who decides to discontinue IP will always be asked about the reason(s) for discontinuation and the presence of any AE. The patient should continue attending subsequent study visits, and data collection should continue according to the study protocol. If the patient does not agree to continue in-person study visits, a modified follow-up must be arranged to ensure the collection of endpoints and safety information. This follow-up could be a telephone contact with the patient, a contact with a relative or treating physician, or information from medical records. The approach taken should be recorded in the medical records. A patient that agrees to modified follow-up is not considered to have withdrawn consent or to have withdrawn from the study.

Patients who are permanently discontinued from further receipt of IP, regardless of the reason, will be identified as having permanently discontinued treatment. Patients who are permanently discontinued will enter follow-up (see the SoAs).

Patients who permanently discontinue drug for reasons other than objective RECIST disease progression should continue to have RECIST scans performed according usual clinical practice, at least q12w \pm 1w (relative to the date of inclusion), until RECIST 1.1-defined radiological PD plus an additional follow-up scan or death (whichever comes first) as defined the SoAs.

If a patient is discontinued for RECIST 1.1-defined progression, then the patient should have 1 additional follow-up scan performed preferably at the next (and no later than the next) scheduled imaging visit, and no less than 4 weeks after the prior assessment of PD.

All patients will be followed for survival until the end of the study.

Patients who decline to return to the site for evaluations should be contacted by telephone as indicated in the SoAs as an alternative.

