PFS (days) = Date of event or Censor date – treatment start date +1

Patients who have not progressed or died at the time of analysis will be censored at the time of the latest date of assessment from their last evaluable assessment. However, if the patient progresses or dies after 2 or more missed visits, the patient will be censored at the time of the latest evaluable assessment prior to the 2 missed visits. If the patient has no evaluable visits or does not have baseline data, he/she will be censored at Day 1 unless he/she dies within 2 visits of baseline, in which case the date of death is the event date.

OS: Defined as the time from the first date of treatment until death due to any cause.

OS (days) = Death date or Censor date - treatment start date +1

Any patient not known to have died at the time of analysis will be censored based on the last recorded date on which the patient was known to be alive.

ORR: Based on Investigator–assessed response to treatment of CR and PR, per RECIST1.1.

DoR: Defined as the time from the date of first documented response per RECIST1.1 until the first date of documented progression per RECIST1.1 or death in the absence of disease progression.

DoR (days) = Date of PFS event or censoring – Date of first response +1

The end of response should coincide with the date of progression or death from any cause used for the PFS endpoint. If a patient does not progress following a response, then the patients' DoR will be censored at the PFS censoring time. DoR will not be defined for those patients who do not have a documented response.

Time to symptom deterioration (EORTC QLC-C30 and QLC-LC13): Defined as the time from start of study drug until the date of the first clinically meaningful symptom deterioration that is confirmed at the subsequent assessment or death (by any cause) in the absence of a clinically meaningful symptom deterioration, regardless of whether the patient withdraws from study drug or receives another anticancer therapy prior to symptom deterioration.

Change from baseline (EORTC QLC-C30 and QLC-LC13, PRO-CTCAE): Defined as the post-treatment value minus the value at baseline. The % change from baseline will be calculated as (postbaseline value - baseline value) / baseline value x 100.

Treatment duration: Defined as Treatment end date - Treatment start date +1; will be summarized.

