Any patient not known to have died at the time of analysis will be censored based on the last recorded date on which the patient was known to be alive. It will be analysed OS, OS at 6 months (6mOS) and OS at 12 months (12mOS) and OS at 18 months (18mOS).

- Time to Treatment Discontinuation (TTD): This analysis will be performed for the Intention-to-Treat population (ITT). TTD is defined as the time from the first date of treatment until date of discontinuation of treatment. Date of discontinuation will be the date reported in end of study form. It will be performed just on the patients that report treatment discontinuation, determined if any of the following occurs:
  - Withdrawal of consent from further treatment with IP.
  - An AE that, in the opinion of the Investigator or AstraZeneca, contraindicates further dosing.
  - Any AE that meets criteria for discontinuation as defined in the Dosing Modification and Toxicity Management Guidelines or as defined in the local prescribing information for the EP treatment.
  - Pregnancy or intent to become pregnant.
  - Non-compliance with the study protocol.
  - Initiation of alternative anticancer therapy including another investigational agent.
  - Clinical progression or confirmed radiological progression and Investigator determination that the patient is no longer benefiting from treatment with IP.

#### 4.2.2.2 Secondary outcome 2

To describe the impact of durvalumab in combination with platinum–etoposide as first-line treatment for patients with ES-SCLC on patients' disease-related symptoms and Health Related Quality of Life (HRQoL) and (PROs).

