- Overall survival (OS): OS will be analyzed using a Kaplan-Meier plots. Summaries of the number and percentage of patients who have died, those still in survival follow-up, those lost to follow-up, and those who have withdrawn consent will be provided along with the median OS and corresponding 95% CI. In addition, the survival rate at 6 (OS 6), 12 (OS 12), and 18 (OS 18) months will be presented.

A subgroup analysis may be conducted comparing OS in the following subgroups, assuming sufficient sample size per subgroup: platinum therapy receiving (carboplatin or cisplatin), age ( $\geq 65$ ,  $< 65$ ), gender, performance status, smoking status, CNS metastasis at baseline (Yes/No) and number of chemotherapy cycles (5 or 6 cycles vs 4 or less cycles)

For each subgroup, the HR and 95% CI will be calculated by Cox regression and a log-rank test will be provided.

- Time to Treatment Discontinuation (TTD): Summaries for the TTD will be provided (continuous data).

### 5.2.2 Secondary outcome 2

To describe the impact of durvalumab in combination with platinum–etoposide as first-line treatment for patients with ES-SCLC on patients' disease-related symptoms and Health Related Quality of Life (HRQoL) and (PROs).

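### Time to treatment discontinuation is defined by stopping treatment, but its date comes from the end-of-study form, which read literally records study exit and lengthens the endpoint

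*SAP*

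**What the plan says.** TTD is listed among the effectiveness endpoints in the protocol synopsis and in protocol Table 3. SAP 4.2.2.1 defines it: "TTD is defined as the time from the first date of treatment until date of discontinuation of treatment". The next sentence names the data source: "Date of discontinuation will be the date reported in end of study form". The analysis is confined to patients who stopped ("It will be performed just on the patients that report treatment discontinuation"), and a list of reasons for stopping follows. SAP 5.2.1 plans descriptive summaries of TTD as continuous data.

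The protocol treats stopping treatment and leaving the study as separate events. Section 7.1.1 states: "Discontinuation of study treatment, for any reason, does not impact the patient's participation in the study". It also states: "All patients will be followed for survival until the end of the study". Section 8.1.2 requires a survival contact every 2 months after treatment stops, and section 4.4 places a patient's completion of the study at the last scheduled visit.

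A treatment-specific end date is already planned. Protocol 9.4 has: "Treatment duration: Defined as Treatment end date - Treatment start date +1". SAP 4.3.4 also computes treatment duration from treatment start and end dates, by phase.

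**The concern.** The definition names a treatment event, but the date is taken from a form whose title refers to the end of the study. A programmer who follows the sentence as written would take the study-exit date. For a patient who stops durvalumab at month 4 because of toxicity and dies at month 14, TTD would be 14 months although treatment lasted 4.

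The error runs one way. For anyone who stops and stays in follow-up, exit comes after the stop, so TTD is lengthened. The endpoint would move towards follow-up time, and the report would contain two measures of time on treatment with different end dates.

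**Working it through.** **Step 1: the texts side by side.** The documents give no planned value for TTD, so there is no figure to reproduce. The check is whether the named date can stand for the defined event.

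| Question | Source | Answer |
|---|---|---|
| What event ends TTD? | SAP 4.2.2.1 | Discontinuation of treatment |
| Where does its date come from? | SAP 4.2.2.1 | End-of-study form |
| Does stopping treatment end participation? | Protocol 7.1, 7.1.1 | No |
| What follows the stop? | Protocol Table 2, 8.1.2 | Safety visits to 3 months, then survival contacts every 2 months |
| When has a patient completed the study? | Protocol 4.4 | At the last scheduled visit |
| Which end date is used for treatment duration? | Protocol 9.4, SAP 4.3.4 | Treatment end date |

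The treatment-stop and study-exit dates coincide only when a patient leaves the study on stopping: by withdrawing all consent, dying on treatment, or still being treated when the study closes. For other patients the two dates differ.

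**Step 2: an illustration of size.** Inputs:

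- Median overall survival 13.0 months, reported for durvalumab plus chemotherapy in the earlier phase III trial (protocol 2.3.1.2).
- Median time to treatment stop 4, 5 or 6 months. This is an assumption, set equal to the 4 to 6 month median time to progression in protocol 2.3.3.
- Uniform accrual over 6 months.
- Follow-up of the last patient for 12 months (last enrolled Q2 2021, last completed Q2 2022 in the synopsis), with 18 and 24 months as assumed alternatives.

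Model: stop time T is exponential with rate ln(2)/m, where m is the median stop time. Survival after the stop, B, is exponential, with its mean chosen so that T + B has median 13.0 months. Study exit is the smaller of T + B and the administrative end. Medians are taken among patients with T before the administrative end, using 400,000 simulated patients per setting.

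| Median stop (assumed) | Last patient followed | Median TTD from stop date | Median TTD from study exit | Difference |
|---|---|---|---|---|
| 4 | 12 | 3.6 | 12.0 | 8.4 |
| 4 | 18 | 3.8 | 12.7 | 8.9 |
| 4 | 24 | 3.9 | 12.9 | 9.0 |
| 5 | 12 | 4.1 | 11.5 | 7.4 |
| 5 | 18 | 4.6 | 12.3 | 7.7 |
| 5 | 24 | 4.8 | 12.7 | 7.9 |
| 6 | 12 | 4.6 | 10.9 | 6.3 |
| 6 | 18 | 5.3 | 11.9 | 6.6 |
| 6 | 24 | 5.6 | 12.4 | 6.8 |

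All values are in months. The differences run from 6.3 to 9.0, and the ratios from 12.4/5.6 = 2.2 to 12.7/3.8 = 3.3.

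**Step 3: limits of the illustration.** The 4 to 6 month figure belongs to chemotherapy, and the 13.0 month figure to durvalumab plus chemotherapy. The model has every patient who stops remain in follow-up and none die on treatment. Protocol 6.1.3 allows treatment beyond RECIST progression, which would make stops later and the gap smaller; in the table, each extra month of median stop time removes about 1 month of difference.

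**The case against.** The best reply is that end of study is loose wording for end of treatment. The sentence leads straight into a list of reasons for stopping treatment, none of which is death or the end of survival follow-up. SAP 4.3.3 summarises performance status at baseline, at the start of each phase and at end of study, with no end-of-treatment timepoint, although protocol Table 1 has an end-of-treatment column. Performance status at true study exit would make little sense when many exits will be deaths or telephone contacts. The form may also hold a treatment-stop date.

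This lowers certainty but does not remove the problem. The eCRF is not available, and nothing in either document says that the form carries the date treatment stopped. If it does, the SAP has to say so.

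A second reply is that a wrong TTD would show up. SAP 4.3.4 reports durvalumab duration, dose and cycles by phase, and SAP 5.1 reports adverse events leading to interruption or discontinuation. That stands: it limits the harm to the overall picture of exposure, but TTD itself would still be wrong.

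A reader might go further and infer that the date is wrong for every patient who stops, or that TTD becomes a copy of survival. The documents do not support either. The dates can coincide (Step 1), administrative closure caps exit times below survival, and the content of the form is unknown. A reader might also subtract medians, 13.0 - 6 = 7 to 13.0 - 4 = 9 months, and take that as the measured error. Those medians come from different treatments, and a difference of medians is not the median difference.

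**Conclusion.** The definition and the date source conflict on the face of the SAP, given a protocol that keeps patients in the study after treatment stops. Followed literally, the rule lengthens TTD for patients who stop and stay in follow-up, and can set it against the treatment-duration tables. That conclusion rests on the text alone.

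The size is not determined by the documents. About 6 to 9 months on the median holds only under the Step 2 assumptions and if the form records study exit alone.

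This should be fixed but is not critical: TTD is one descriptive secondary endpoint in a study without a formal hypothesis, and neither primary safety endpoint depends on it. Restricting TTD to patients who discontinued, without censoring, is a different issue that pulls towards shorter times; it does not correct the date.

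**What to change.** In SAP 4.2.2.1, replace the sentence on the date source with:

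> Date of discontinuation is the date of permanent discontinuation of study treatment, taken from the treatment administration/discontinuation record (the treatment end date used in SAP 4.3.4 and protocol 9.4), being the latest end date across the study treatment components (durvalumab, etoposide, platinum). This is the last-dose date.

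The component has to be named because SAP 4.3.4 has no single treatment end date: it works by phase and, during chemotherapy, separately for each drug. The last-dose statement is needed because the decision to stop can come later than the last dose. Use the end-of-study form only for study completion status. How death on treatment is counted is a separate question of definition and need not be settled to correct the source.

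The cost is one SAP amendment and a change to one derivation. Protocol 6.3 already requires dose discontinuations to be recorded in the eCRF, and the treatment end date is already needed for the duration tables. TTD is not among the interim outputs listed in SAP section 7. The reported TTD will be shorter wherever the form would have supplied a later exit date.
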